**6. SPECIFIC AIMS**

The major objective of this proof-of-concept study is to gain clinical evidence to utilize Ivabradine as a treatment option for POTS. Preliminary data indicates that such an expectation is possible given the fact that Ivabradine has been proven to decrease heart rate.

We will conduct a randomized double-blind placebo controlled clinical trial with a double cross over design. 20 patients with POTS will receive Ivabradine treatment vs placebo for one month. Then there will be a one-week wash out period prior to the cross over in which patients who received Ivabradine will receive the placebo, and patients who initially were on placebo will now receive Ivabradine. We will compare heart rates in both groups after one-month of intervention. We will assess if Ivabradine mitigates patient symptoms and increases patient adherence. This work will help translate our research on beneficial effects of Ivabradine into a clinically relevant patient population.

We will test this hypothesis by pursuing the following aim:

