### **Specific Aim 1: Evaluate the change in heart rate**

*Hypothesis: Ivabradine will reduce tachycardia and improve functional status in patients with POTS.*

We propose to test this hypothesis in a randomized double-blind placebo-controlled with a cross over clinical trial in which otherwise healthy patients diagnosed with POTS will be randomized into Ivabradine or placebo group treatment for one month then crossed over to the other group for another month (one week wash-out period before cross over). Patients will undergo a baseline tilt table test, norepinephrine bloodwork, and quality of life (QOL) questionnaires.

- Primary endpoint:
  - Change in heart rate after one month of Ivabradine intervention compared to baseline.
- Secondary endpoint:
  - Quality of life measured with questionnaires after one month of Ivabradine intervention compared to baseline.

We will assess:

- *Effects on tachycardia (table tilt test)*
- *Orthostatic heart rate monitoring*
- *Symptomatic changes (QOL questionnaire)*

*Results will provide significant understanding of mechanisms that underlie sympathetic hyperactivation and provide a potential avenue for an effective and safe treatment with Ivabradine with the ultimate goal of increasing patient adherence and reducing debilitating patient symptoms.*

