## **9. RESEARCH DESIGN AND METHODS**

**Overall Study Design.** The clinical trial will be registered under [www.clinicaltrials.gov](http://www.clinicaltrials.gov). Subjects between the ages of 18-65 who have a POTS diagnosis will be enrolled. Specifically, we will enroll patients who have hyperadrenergic POTS as confirmed by norepinephrine (NE) levels > 600 pg/ml. This is a 3-month study with a randomized double-blind placebo controlled cross over design. Subjects will be randomized into one of two groups (Ivabradine or placebo for one-month) then crossed over after a one-week washout period to the other group for one-month. Refer to Figure 1 below for details.

[figure not shown]

Figure 1. Randomized double-blind placebo-parallel group crossover trial with Ivabradine for patients with POTS.

**Study Visits.** There will be seven visits at the ACTRI and UCSD Cardiology clinics.

-Visit 1 is the pre-screening visit during which norepinephrine (NE) blood results will be obtained to confirm hyperadrenergic POTS diagnosis (NE> 600pg/ml). Orthostatic heart rate will be monitored. A urine pregnancy test will also be administered at this time. Post-menopausal women and women who are infertile will not be asked to take pregnancy test per PI discretion.

-At Visit 2, baseline lab work will be obtained to assess cardiometabolic health (CBC, CMP, TSH, T4, BNP). A tilt table test will be performed to determine baseline heart rate and QOL questionnaire (ShortForm36, SF36) will be completed. Orthostatic heart rate will be monitored. At this point, the patient will be randomized into the Ivabradine or placebo group for one month.

-At Visit 3, two-weeks into treatment, the patient will return to ACTRI for drug titration. Orthostatic heart rate will be monitored. If the patient fulfills criteria (see **Ivabradine Dosing** below), they will either increase, decrease, stop, or not change their Ivabradine dose.

-At Visit 4, one month after starting the current treatment, orthostatic heart rate monitoring, NE bloodwork, and QOL questionnaires will be completed. There will be a one-week wash-out period before the patient crosses over to the other group for one month.

-At Visit 5, the patient will return for orthostatic heart rate monitoring, NE bloodwork, and QOL questionnaires. A urine pregnancy test will be administered at this time. Post-menopausal women and women

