**Statistical Analysis.** Continuous variables including mean heart rate, maximum heart rate, and quality of life scores will be summarized using descriptive statistics, including the number of observation (n) mean, standard deviation (SD), standard error (SE), median, the 1st (Q1) and 3rd (Q3) quartiles, minimum, and maximum values. The change in heart rate at one month from baseline will be compared by T-tests based on treatment status with placebo versus Ivabradine. Categorical variables will be compared by McNemar's test based on treatment status with placebo versus Ivabradine.

The study design will be adaptive and data analysis will be done in batches. The PI and others involved in data analysis will be blinded to who is the Ivabradine group and who is in the placebo group.

**Power Analysis.** Assuming a decrease in average heart rate of 10 beats/min is clinically significant (e.g. Decrease from 100 to 90; magnitude of effect 10%) with power 0.8 and standard deviation in heart rate is 7.5 beats/min, the estimated sample size is 18 patients. We will enroll 10 patients in each group to account for the 10% drop-out rate and to ensure the study is adequately powered. For sample size calculation, two-sided alpha level = 0.05 and two sample t-test are used.

**Drop-outs.** If any patient decides to withdraw from the study due to the intolerance of side-effects, we will try to obtain a tilt table test, orthostatic heart rate, QOL questionnaire, and blood tests at the time of drop-out.

**Documentation.** All patient related documentation will be stored at UCSD for future analysis as funding becomes available. To minimize the potential loss of confidentiality, patients will be assigned a unique number as their subject identifier code. The unique subject code will be used to label all study documents. The key that relates the code numbers to the individuals will be kept in a locked cabinet in the PI's office at the ACTRI.

All procedures mentioned above are research procedures and are not part of standard care.

Results may be used for diagnosis, treatment, and prevention of disease in patients.

**Incidental findings that result from the conduct of this study that require medical intervention for the subject will be noted by the PI or her project's medical research staff. They will refer the subject to his primary care physician. If the subject does not have a primary care physician one will be appointed for him or her.**

---

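### The SF-36 secondary endpoint compares the ivabradine month with baseline, and no comparison of SF-36 with placebo is specified

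*Combined protocol and SAP*

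**What the plan says.** All references are to the combined protocol and SAP.

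- **Endpoint.** Section 6, Specific Aim 1, gives the secondary endpoint as "Quality of life measured with questionnaires after one month of Ivabradine intervention compared to baseline". The primary endpoint, on heart rate, is also worded as a change from baseline under ivabradine.
- **Analysis.** In Section 9, Statistical Analysis, "quality of life scores will be summarized using descriptive statistics". The only treatment comparison named there for a continuous variable concerns heart rate: "The change in heart rate at one month from baseline will be compared by T-tests based on treatment status with placebo versus Ivabradine". McNemar's test is reserved for categorical variables, and the same paragraph classes quality-of-life scores as continuous.
- **Aims.** The introduction to Section 6 says "We will compare heart rates in both groups after one-month of intervention". It also says that symptoms will be assessed, but names no comparator for them.
- **Collection.** In Section 9, Study Visits, SF-36 is completed at Visit 2 ("QOL questionnaire (ShortForm36, SF36) will be completed"), at Visit 4 ("one month after starting the current treatment, orthostatic heart rate monitoring, NE bloodwork, and QOL questionnaires will be completed"), after washout ("At Visit 5, the patient will return for orthostatic heart rate monitoring, NE bloodwork, and QOL questionnaires") and again at Visit 7, the end of the second period. The Specific Protocols paragraph confirms collection before and after each period and describes the instrument as subjective.
- **Blinding of analysts.** Section 9 states that "The PI and others involved in data analysis will be blinded to who is the Ivabradine group and who is in the placebo group".

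**The concern.** The hypothesis in Specific Aim 1 has two parts: less tachycardia and better functional status. SF-36 is the only questionnaire named that can speak to the second part, and it is self-reported. A change from baseline under ivabradine mixes any drug effect with placebo response, drift over time and regression to the mean. A placebo-controlled crossover exists to separate these, and the end-of-placebo scores needed to do so are collected in the same patients. The endpoint as defined leaves them out.

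If nothing is specified, the choice between a before-after change and a placebo contrast, and the form of that contrast, stays open until the data are in hand. The trial could then report improved quality of life on ivabradine without showing that placebo did any less.

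**Working it through.** **1. Is an SF-36 contrast with placebo specified anywhere?**

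| Place | Heart rate | SF-36 |
|---|---|---|
| Section 6, introduction | groups compared | symptoms assessed, no comparator |
| Specific Aim 1, endpoints | versus baseline | versus baseline |
| Section 9, Assessments | before and after treatment | before and after treatment |
| Section 9, Statistical Analysis | t-test, placebo versus ivabradine | descriptive summary |

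For heart rate, the last row supplies the control that the endpoint wording lacks. Nothing does so for SF-36.

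**2. Which visit is baseline?** Take one month as 4 weeks and the washout as 1 week.
- Visit 2 as baseline: the change spans 4 weeks if ivabradine comes first and 4 + 1 + 4 = 9 weeks if placebo comes first.
- Start of each period as baseline (Visit 2 or Visit 5): 4 weeks in both sequences.

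Neither reading brings in placebo. Under the first, elapsed time also differs between sequences.

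**3. How much of the data does the endpoint use?** Sections 10 and 11 expect 18 patients in the final analysis. That number comes from the heart-rate power calculation and can be reproduced: 2 × (7.5 × (1.960 + 0.842)/10)² = 8.83, so 9 per group and 18 in total; 18/0.9 = 20 to enrol. No SF-36 calculation is given.
- Questionnaires planned: 18 × 4 visits = 72.
- Used by the endpoint: 18 × 2 = 36.
- End-of-placebo scores used: 0 of 18.

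**4. What precision would the placebo contrast have?** Let SD be the standard deviation of a single SF-36 score and r a common correlation between visits. Neither is in the documents, so r is varied and results are in SD units. The within-patient difference has SDd = SD × √(2(1 − r)). The period-adjusted estimate has SE = 0.5 × SDd × √(1/n1 + 1/n2) on n1 + n2 − 2 degrees of freedom. With 9 patients per sequence, SE = 0.2357 × SDd and t(0.975; 16) = 2.120, so the 95% half-width is 0.4997 × SDd.

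| r (assumed) | SDd / SD | half-width, 9/9 | half-width, 10/8 |
|---|---|---|---|
| 0.3 | 1.183 | 0.591 SD | 0.595 SD |
| 0.5 | 1.000 | 0.500 SD | 0.503 SD |
| 0.7 | 0.775 | 0.387 SD | 0.389 SD |
| 0.8 | 0.632 | 0.316 SD | 0.318 SD |

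**5. What could go wrong if the before-after change were tested?** The plan names no such test, so this is illustration only. Assume no drug effect, 18 completers, a two-sided paired t-test at 0.05 and r from 0.3 to 0.7. A non-drug improvement of 0.2, 0.3 or 0.5 SD would be declared significant in 10–18%, 17–34% or 39–73% of trials, against a nominal 5%. The ivabradine-minus-placebo contrast removes any shift common to both periods.

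**The case against.** The strongest reply is that the two endpoints share one form of words. For heart rate, that wording evidently describes the variable, and Section 9 supplies the treatment comparison. The same could be meant for SF-36, the more so because Specific Aim 1 says the whole hypothesis, functional status included, will be tested in a placebo-controlled crossover. On this view the only gap is a missing sentence in Section 9. It is true that the intention was probably a controlled comparison. But the design sentence names no contrast or method, and the only rule actually stated for SF-36 is the one against baseline.

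Second, blinded analysts will very likely summarise SF-36 under both treatments, so the placebo scores need not go unseen. That is fair. Side-by-side summaries are still not a within-patient contrast with an interval.

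Third, this is a secondary outcome in a 20-patient proof-of-concept study, and describing such an outcome without a formal test is acceptable. That bears on the weight of the point. It is also a reason to report an estimate with an interval.

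Three smaller points stand in part. The documents tie SF-36 to symptoms, so its link to functional status is inferred. Visit 2 is the more natural baseline, since no section calls Visit 5 one. And the plan does not say which SF-36 scale or summary score is the endpoint, which the fix must settle.

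**Conclusion.** The concern holds. As written, the SF-36 endpoint is a before-after change under ivabradine, and no section specifies a comparison of SF-36 with placebo. The endpoint could not separate a drug effect from placebo response or time effects, although the scores that would do so are collected at Visits 4 and 7.

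The size of any bias is unknown. The countable facts are 36 of 72 questionnaires used and none of the 18 end-of-placebo scores, assuming 18 patients complete all four SF-36 visits. The half-widths of 0.59 to 0.32 SD describe the replacement contrast, not the defect. They rest on the assumed correlations, 9 completers per sequence and no carryover.

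This should be corrected, but it concerns a secondary endpoint. For heart rate the mismatch is one of wording only.

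**What to change.** - In Specific Aim 1, redefine the secondary endpoint as the within-patient difference in SF-36 between the end of the ivabradine month and the end of the placebo month (Visits 4 and 7, ordered by sequence). Name the SF-36 scale or summary score.
- In Section 9, Statistical Analysis, specify a period-adjusted crossover analysis of that difference with a 95% confidence interval. State that it assumes no carryover across the one-week washout.
- Keep change from baseline as description, and say which visit is baseline. If baseline is Visit 2, it cancels from the within-patient contrast: (ivabradine − Visit 2) − (placebo − Visit 2) = ivabradine − placebo. End-of-period scores therefore lose nothing relative to changes from Visit 2.
- Align the primary endpoint wording in Specific Aim 1 with the placebo comparison of heart rate already in Section 9.

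The cost is wording and one more analysis of data already planned. No visit, measurement or patient is added. The change should be made before the treatment codes are broken.

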## **7. BACKGROUND AND SIGNIFICANCE**

Given that the etiology of POTS is complex, there are currently no Class I recommendations for its treatment. POTS has five pathophysiological subtypes 1) hyperadrenergic, 2) peripheral autonomic denervation, 3) hypovolemic 4) deconditioning, 5) anxiety, and hypervigilance. Among the clinical subtypes, the most common form of POTS is hyperadrenergic (comprising up to 50% of POTS patients). At the cellular level hyperadrenergic POTS is thought to be associated with an increase in hyperpolarization-activated cyclic nucleotide-gated (HCN) channel expression in the sinus node due to an increase in sympathetic activation. The increased sympathetic activity is also associated with elevated norepinephrine levels from a norepinephrine transporter defect, which may have a genetic component. Ivabradine selectively blocks the HCN channel within the SA node resulting in lower heart rate and we hypothesize that it will be beneficial in lower heart rate in patients with POTS that have upregulation in HCN channel expression.

The current standard of care in establishing the diagnosis of POTS is assessing if there is a significant increase in heart rate upon standing or with a tilt table test. The criteria for an augmented heart rate increase is prolonged heart rate increase of greater than 30 beats/min or an increase to 120 beats/min within the first ten minutes of a tilt table test without postural hypotension. Prior to diagnosis of POTS autonomic neuropathies, central dysautonomias, bedrest deconditioning, and dehydration need to be ruled out.

Currently, there are no Class I recommendations for the treatment of POTS. Class II recommendations include: exercise (level B-R), IV saline for acute decompensation (level E), fludrocortisone and pyridostogmine (level C), increased salt and fluid intake, Midodrine or low dose-beta-blocker (level B), and clonidine or methyldopa (level E) for central hyperadrenergic POTS. Florinef and midodrine are most commonly prescribed for these patients but most do not tolerate the side effects. Florinef increases blood volume by increasing the sensitivity of blood vessels to catecholamines; side effects include but are not limited to supine hypertension, hypokalemia, ankle edema, and congestive heart failure. Midodrine works as an alpha-1 adrenergic agonist that does not cross the blood brain barrier; its side effects include piloomotor reactions, supine hypertension, gastrointestinal issues, and urinary retention. There is a great unmet clinical need for an effective intervention in these patients.

Several case reports have shown that Ivabradine is effective in dramatically lowering heart rate in POTS patients, but none have been performed in a randomized clinical trial setting with a placebo group. For example, Ewan et al documented the significant reduction in heart rate in a 15 year old female patient with POTS as a result of Ivabradine consumption that was accompanied by improvements in fatigue and blood pressure remained stable.

Also, Hersi was able to demonstrate that Ivabradine (5mg twice daily) completely alleviated the symptoms (weakness, palpitations, tingling/coldness in feet) of a 25 year old female patient with POTS. It is noteworthy to mention that when she ran out of the medication, her symptoms returned, but were quickly mitigated when Ivabradine was reinstated. Such reports validate that Ivabradine poses as an effective treatment option for POTS patients.

Additionally, the retro-perspective study conducted by McDonald et al identified and analyzed twenty patients who were prescribed Ivabradine (2.5mg once daily) specifically for POTS; this provided valuable insight for utilizing Ivabradine as a treatment option for POTS. McDonald et al concluded that 55% of patients who continued to take Ivabradine reported a decrease in palpitations and tachycardia episodes and 44% of those patients reported a decrease in fatigue. These improvements in fatigue symptoms are consistent with the findings of Ewan et al. However, 20% of these patients were also taking floninef or midodrine in conjunction with Ivabradine, which may have confounded the true efficacy of Ivabradine. Nonetheless, they were able to show that Ivabradine was well-tolerated in patients with POTS and the adverse side effects were minimal.

Similarly, Sutton et al prescribed Ivabradine (5mg twice daily) to twenty POTS patients and concluded that there were notable benefits in terms of reducing palpitations and vasovagal syncope over the course of eighteen months for eighteen patients; two patients discontinued due to lack of benefit.

Moreover, Barzilai et al performed an open-label trial without a placebo group in which they concluded that a single dose of 7.5mg Ivabradine significantly lowered the heart rate of POTS patients without any adverse side-effects. They also noted that Ivabradine maintained the sympathovagal balance despite the significant difference in heart rates between baseline and treatment; they postulate the dosing may be a contributing factor.

Furthermore, many of these prior studies strongly recommend the need for a randomized double-blind placebo-controlled clinical trial in order to measure the efficacy and effectiveness of only prescribing Ivabradine to patients with POTS. Thus, based on prior studies, the goal of this proposal is to evaluate a potentially effective treatment method for POTS with Ivabradine.

## **8. PROGRESS REPORT**

None.

## **9. RESEARCH DESIGN AND METHODS**

**Overall Study Design.** The clinical trial will be registered under [www.clinicaltrials.gov](http://www.clinicaltrials.gov). Subjects between the ages of 18-65 who have a POTS diagnosis will be enrolled. Specifically, we will enroll patients who have hyperadrenergic POTS as confirmed by norepinephrine (NE) levels > 600 pg/ml. This is a 3-month study with a randomized double-blind placebo controlled cross over design. Subjects will be randomized into one of two groups (Ivabradine or placebo for one-month) then crossed over after a one-week washout period to the other group for one-month. Refer to Figure 1 below for details.

[figure not shown]

Figure 1. Randomized double-blind placebo-parallel group crossover trial with Ivabradine for patients with POTS.

**Study Visits.** There will be seven visits at the ACTRI and UCSD Cardiology clinics.

-Visit 1 is the pre-screening visit during which norepinephrine (NE) blood results will be obtained to confirm hyperadrenergic POTS diagnosis (NE> 600pg/ml). Orthostatic heart rate will be monitored. A urine pregnancy test will also be administered at this time. Post-menopausal women and women who are infertile will not be asked to take pregnancy test per PI discretion.

-At Visit 2, baseline lab work will be obtained to assess cardiometabolic health (CBC, CMP, TSH, T4, BNP). A tilt table test will be performed to determine baseline heart rate and QOL questionnaire (ShortForm36, SF36) will be completed. Orthostatic heart rate will be monitored. At this point, the patient will be randomized into the Ivabradine or placebo group for one month.

-At Visit 3, two-weeks into treatment, the patient will return to ACTRI for drug titration. Orthostatic heart rate will be monitored. If the patient fulfills criteria (see **Ivabradine Dosing** below), they will either increase, decrease, stop, or not change their Ivabradine dose.

-At Visit 4, one month after starting the current treatment, orthostatic heart rate monitoring, NE bloodwork, and QOL questionnaires will be completed. There will be a one-week wash-out period before the patient crosses over to the other group for one month.

-At Visit 5, the patient will return for orthostatic heart rate monitoring, NE bloodwork, and QOL questionnaires. A urine pregnancy test will be administered at this time. Post-menopausal women and women

who are infertile will not be asked to take pregnancy test per PI discretion. The patient will be instructed to begin the secondary treatment (placebo or Ivabradine) for one month.

-At Visit 6, two-weeks into this treatment, the patient will return to ACTRI for drug titration. Orthostatic heart rate will be monitored. If the patient fulfills criteria (see **Ivabradine Dosing** below), they will either increase, decrease, stop, or not change their Ivabradine dose.

-At Visit 7, one month after starting the secondary treatment, the patient will return for orthostatic heart rate monitoring, NE bloodwork, and QOL questionnaires.

Blood samples will be saved and securely stored with the PI for future research analysis and purposes.

**Randomization.** Randomization refers to the order in which patients receive placebo or Ivabradine. If a patient receives Ivabradine first for one month, then he/she will be switched over to placebo for one month. If a patient receives placebo first for one month, then he/she will be switched over to Ivabradine for one month. There will be a one-week washout period prior to the cross-over. There will be 10 patients in each group.

**Ivabradine Dosing.** Ivabradine dose will initiate at 5mg twice daily (bid) and be increased to 7.5mg twice daily (bid) after 2 weeks if the heart rate is greater than 70 beats/min. If the heart rate is less than 70 beats/min there will no increase in dose. If the heart rate is less than 50 beats/min, or if the patient has symptoms of dizziness or lightheadedness, then Ivabradine will be stopped.

If patients have side effects and feel that cannot continue with Ivabradine we will decrease the dose from 7.5mg bid to 5mg bid (or if they are on 5mg bid to 2.5mg bid). After this dose reduction if the patient is still unable to tolerate Ivabradine, we will stop Ivabradine and withdraw patient from the study. If a patient is unable to tolerate Ivabradine (particularly prior to crossover period), he/she will be withdrawn. The starting dose and titration model is the same for the crossover treatment period as the initial month.

In our clinical experience using Ivabradine in patients with inappropriate sinus tachycardia (which are very similar to POTS patients in age and co-morbidities) we have not seen significant side effects that have caused patients to stop the drug. Refer to the uploaded Ivabradine Drug Information document for more details.

**Specific Protocols.** Brief synopsis of methods currently used is provided below.

**Tilt Table Test:** Only the physician PIs will perform the tilt table test with assistance from the medical staff of the UCSD Medical Center.

**Orthostatic Heart Rate Monitoring:** First, the patient's heart rate will be measured at rest after lying down for 3 minutes. Then, the patient will be asked to stand and the standing heart rate will be measured after 3 minutes. The changes in position with 3 minute intervals will establish the orthostatic heart rate.

**Quality of Life (QOL) Questionnaire:** Patients will complete the Short Form-36 (SF36) subjective questionnaire to aid in analysis of patient symptoms before/after each treatment period.

**Blood Tests:** The following blood tests will be processed at UCSD Clinical Laboratories: 1) Cardiometabolic parameters: (CBC, CMP, TSH, T4, BNP) and 2) norepinephrine levels (NE).

The 2-3-month time period will be used as prior literature suggests that this length of therapy is needed to trigger pharmaceutical changes to translate into functional endpoints.

**Assessments.** We will assess for patient improvement with tilt table testing, orthostatic heart rate monitoring, labs, and quality of life (QOL) questionnaires before and after treatment. The patient will undergo a baseline norepinephrine workup and a baseline tilt table test; if the patient is on Midodrine, Florinef, or Ivabradine, there will be a one week washout period. The patient will then be randomized into the Ivabradine or the placebo group for one month. After this one month, they will undergo orthostatic heart rate monitoring, blood work for norepinephrine levels, and QOL questionnaires. There will be a one week washout period before they are crossed over to the other therapy (placebo vs Ivabradine) for one month. The washout period protocol

---

includes maintaining a stable salt and fluid intake. Once crossed over, they will repeat an orthostatic heart rate monitoring, blood work for norepinephrine levels, and QOL questionnaires.

We will continuously assess for all adverse events throughout the study. Some of these labeled adverse reactions may include bradycardia, hypertension, atrial fibrillation, and visual distortions (visual brightness, diplopia, visual impairment, phosphenes).

**Statistical Analysis.** Continuous variables including mean heart rate, maximum heart rate, and quality of life scores will be summarized using descriptive statistics, including the number of observation (n) mean, standard deviation (SD), standard error (SE), median, the 1st (Q1) and 3rd (Q3) quartiles, minimum, and maximum values. The change in heart rate at one month from baseline will be compared by T-tests based on treatment status with placebo versus Ivabradine. Categorical variables will be compared by McNemar's test based on treatment status with placebo versus Ivabradine.

The study design will be adaptive and data analysis will be done in batches. The PI and others involved in data analysis will be blinded to who is the Ivabradine group and who is in the placebo group.

**Power Analysis.** Assuming a decrease in average heart rate of 10 beats/min is clinically significant (e.g. Decrease from 100 to 90; magnitude of effect 10%) with power 0.8 and standard deviation in heart rate is 7.5 beats/min, the estimated sample size is 18 patients. We will enroll 10 patients in each group to account for the 10% drop-out rate and to ensure the study is adequately powered. For sample size calculation, two-sided alpha level = 0.05 and two sample t-test are used.

**Drop-outs.** If any patient decides to withdraw from the study due to the intolerance of side-effects, we will try to obtain a tilt table test, orthostatic heart rate, QOL questionnaire, and blood tests at the time of drop-out.

**Documentation.** All patient related documentation will be stored at UCSD for future analysis as funding becomes available. To minimize the potential loss of confidentiality, patients will be assigned a unique number as their subject identifier code. The unique subject code will be used to label all study documents. The key that relates the code numbers to the individuals will be kept in a locked cabinet in the PI's office at the ACTRI.

All procedures mentioned above are research procedures and are not part of standard care.

Results may be used for diagnosis, treatment, and prevention of disease in patients.

**Incidental findings that result from the conduct of this study that require medical intervention for the subject will be noted by the PI or her project's medical research staff. They will refer the subject to his primary care physician. If the subject does not have a primary care physician one will be appointed for him or her.**

---

